3.1 Statistical Analysis

The data analyst will be blinded to the cup assignment. We will use generalized estimating equations for a crossover design to assess intake, spillage, and feeding duration and a sign test to assess the caregiver’s preference. Covariates may include factors such as amount of prior feeding, type of nutrition, number of prior cup feeds with assigned cup, and number of cup feeds between measured feedings. Most covariates typically accounted for (maternal age, other demographics) will not be included because the comparison is the same caregiver/infant pair.

We will conduct exploratory analyses stratifying on age (0-14 days and 15-28 days) and gestational age (<34 weeks and 34-36 weeks) to evaluate potential effect modification by these factors. These are exploratory since this study was not powered to detect effect modification. For each cup separately, we will compare estimates for those assigned the cup first to estimates for those assigned the cup second to evaluate for design effects. If design effects are observed we will analyze our data comparing those first assigned the Nifty cup to those first assigned to the medicine cup, dropping the data from the second cup and removing the cross over design from our study. We will use Stata 13.0 for all statistical analysis. Consistent with our power calculations, a two-sided p-value of 0.05 will be used.

A strength of our statistical approach is that participants with outcome data for at least one feeding assessment are able to be included in our GEE analyses even if other time points are missing. We will evaluate the potential effect of other missing data on our associations using multiple imputation methods.¹²

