5.0 Study procedures

Study participants will be asked to cup feed their infant with the generic cup and the Nifty Feeding Cup in the randomized order assigned. The caregiver will feed their infant with each cup at least 2 times before we measure feedings with the cup. Mothers will not be asked to exclusively cup feed during this study. Preterm infants started on cup feeding will typically start with a cup and then gradually transition to breastfeeding. Mothers are counseled to attempt breast feeding while their infant is using the feeding cup. Study procedures are aligned with KATH practice so the mother will not do anything different than what is clinically indicated as best for mother and baby.

Since infant participants are inpatients, the term ‘visit’ is meant loosely to indicate the sequential study activities that will take place. Research staff may check-in with the caregiver at any time during the participation in the study to coordinate study activities. The day and time of each study visit is an estimate but each visit will be completed before the next. To ensure the infant is clinically indicated to cup feed, prior to each feed we measure, the research assistant (RA) will consult with a provider to make sure the infant can be cup fed.

The caregiver will feed their infants the type of milk/formula in amounts determined by the clinical provider. The study team will not be involved in providing guidance regarding type of milk or amount recommended other than tracking it.

If the infant and/or caregiver have health, social or other problems that arise in the course of study participation that prevent either of them from participating in study visits, we will discontinue them from the study

Details of the tools (e.g. Surveys) and procedures (e.g. Feeding Assessment) used at each visit are outlined in Section 6 below. Also refer to the **Schematic of Study Procedures** found

immediately after the Protocol Summary and the **Visit Activities Schedule**, an Appendix to the protocol.

We estimate the RAs will each be able to manage a workload of 2-3 participants per week and that based on this rate, it will take about 1 year to complete enrollment and data collection activities.

Study participants will be discharged from hospital when clinically appropriate. Participants will not be retained in hospital to finish the study procedures.

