5.2.2 Outcomes

Outcomes related to intake, spillage, and duration will be measured at each Feeding Assessment, which will take place at Visit 2 through 5. Caregiver satisfaction will be measured during Feeding Assessment related to the experience of that feed (V2-V5). Caregiver satisfaction will be measured with the In-Hospital Preference Survey (V5) and the Follow-up Survey (V6).

Milk Intake. We will measure amount (in ml) and weight (in grams) of milk in the cup before the feeding. We will measure the amount and weight of milk in the cup after the feeding. If the cup is refilled, we will measure the amount and weight before and after the refill. The amount and weight will be recorded on the Feeding Assessment case report form. We will use a digital scale

to determine all weight measurements. The weight per ml will be estimated based on the baseline measure and used to adjust the gross measure of intake by subtracting out spillage that occurred during the feed. We will calculate intake per feed from these measures less the amount spilled.

Spillage. We will account for spillage of milk by using a baby bib cloth for all feedings. Each caregiver-infant pair will be provided with a bib cloth for each observed feeding. The bib cloth will be weighed before and after each feed and the weights recorded on the Feeding Assessment form. The difference between the pre and post weights will be used as the measure of the amount spilled. A digital scale will be used and milk weight will be in grams. Spillage will be reported as a percent with the amount of milk in grams spilled/mopped up divided by the total amount of milk weighed in grams less the total amount of milk not used.

Caregiver Satisfaction. Our primary measure of caregiver's satisfaction will be the cup she prefers [secondary] and rated satisfaction [primary] which will be recorded in the In-Hospital Preference Survey completed after the caregiver has finished the feeding portion of the study (V5). A secondary measure will be what the caregiver reports uses most of the time measured in the Follow-up Survey 4 weeks post-discharge (V6). We will also measure the caregiver's satisfaction with each cup after each feeding measured in the Feeding Assessment and in the In-Hospital Preference Survey (V2-V5).

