5.2.3 Case Report Forms

Case report forms will record intervention and outcome data as well as data on other covariates.

Baseline Survey, V1. The baseline intake will record cup assignment, infant weight, length, demographics and infant and maternal feeding and health characteristics (e.g. co-morbidities, type of delivery, etc). It is estimated to take about 10-15 minutes to complete.

Feeding Assessment, V2-V5. This case report form will be used to record outcome information collected on milk intake, spillage and duration of feed and the cup used described below and caregiver's immediate experience using the cup. It will also collect information about prior feedings and time since last feed. Each Feeding Assessment will last as long as the feeding plus about 5 minutes.

In-Hospital Preference Survey, V5. This survey will collect information on the caregiver's experience using both cup and her preferences. It will take about 5 minutes to complete.

Follow-up Survey, V6. This survey will assess cup feeding practices, infant health, and maternal satisfaction with the cup. It will take about 10 minutes to complete.

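### The first-cup-only fallback cannot remove the second cup's influence from the primary satisfaction rating, and the plan does not link the usable V2-V3 ratings to it

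*Combined protocol and SAP*

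**What the plan says.** - **Status of the outcome.** Section 2.2 lists greater caregiver satisfaction as the second primary hypothesis.
- **Primary measure.** Section 5.2.2 tags as primary "rated satisfaction [primary] which will be recorded in the In-Hospital Preference Survey completed after the caregiver has finished the feeding portion". Section 5.2.3 says this survey covers the caregiver's "experience using both cup and her preferences". The Visit Activities Schedule places it at V5 only.
- **Other satisfaction data.** Section 5.2.2 also provides for "satisfaction with each cup after each feeding measured in the Feeding Assessment", at V2 to V5. These ratings are not called primary.
- **Order of events.** Under Section 5.1.3, Cup 1 is removed and Cup 2 provided at V3, listed after that visit's Feeding Assessment. V4 and V5, both on Day 2, are the Cup 2 feeds.
- **Fallback.** Under Section 3.1, if design effects are observed, the groups are compared on their first-assigned cup, "dropping the data from the second cup and removing the cross over design from our study". No outcome is exempted.
- **Power.** Section 2.3 gives 80% power if carryover is observed and says the calculation also applies to satisfaction.

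**The concern.** A first-cup-only analysis is valid because first-period data are recorded before the other treatment has been met. That depends on when the measurement was taken, not on which cup it describes. A V5 rating of Cup 1 describes the first cup but is given after the second has been used. Dropping the second-cup records leaves that rating unchanged.

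If order effects appeared and the rule were followed as written, one of the two primary hypotheses would be tested on data that still carry the effect the rule is meant to remove. Nothing in the output would show this, because the sample size and nominal power would look as planned.

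**Working it through.** **1. Which first-cup values exist before Cup 2 is used**

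| Outcome | When the Cup 1 value is recorded | Before Cup 2 is used? |
|---|---|---|
| Spillage, intake, duration | V2, V3 | Yes |
| Satisfaction, Feeding Assessment (not primary) | V2, V3 | Yes |
| Satisfaction, In-Hospital Preference Survey (primary) | V5 | No |

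From the intervals in Section 5.1, V3 to V5 is more than 4 h + more than 2 h = more than 6 h. The caregiver is to feed with Cup 2 at least twice before V4, and has the measured feeds at V4 and V5 as well.

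**2. What the fallback would estimate**

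Let m_N and m_G be the mean satisfaction with the Nifty and generic cups before any second cup is used. Let c_N be the shift in the Nifty rating after the caregiver has gone on to use the generic cup, and c_G the shift in the generic rating after she has gone on to use the Nifty.

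- Fallback with V5 ratings: (m_N + c_N) − (m_G + c_G) = (m_N − m_G) + (c_N − c_G).
- Fallback with V3 ratings: m_N − m_G.

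A recall effect common to both groups cancels. A contrast effect does not: if a first cup looks better after a worse one and worse after a better one, c_N and c_G have opposite signs and add. The documents give no value for c_N − c_G. On the plan's own scale, each 1 unit of it would be 1/5 = 20% of the 5-unit target difference.

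**3. The plan's own power figure for the fallback**

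Inputs from Section 2.3: 150 pairs, difference 5 (the 5% read as 5 units on the scale of the SD), SD 11, two-sided alpha 0.05. Equal allocation to the two orders, 75 v 75, is assumed.

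- Standard error = 11 × √(2/75) = 1.796.
- 5 / 1.796 = 2.784, and 2.784 − 1.960 = 0.824.
- Power = Φ(0.824) = 79.5%, or 79.0% with the noncentral t.

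The stated 80% reproduces as a two-group comparison. With 200 pairs (100 v 100) it is 89.5%, or 89.2% with t.

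**4. Power if the pre-crossover rating is named instead**

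- One rating per pair (V3): unchanged, 79.0% to 79.5%.
- Mean of V2 and V3: SD = 11 × √((1 + r)/2), where r is the correlation between a caregiver's two ratings. The documents give no r, so a range is assumed:

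| r (assumed) | SD of mean | Power, 75 v 75 (t) |
|---|---|---|
| 0.2 | 8.52 | 94.6% |
| 0.5 | 9.53 | 89.1% |
| 0.8 | 10.44 | 83.0% |

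SD 11 is a cup-feeding figure. The documents give no scale or SD for satisfaction, so these values show only that moving to V3, or to V2 and V3, costs no power on the plan's own terms.

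**5. Pairs who leave before V5**

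Section 5.0 says "Participants will not be retained in hospital to finish the study procedures", so some pairs may lack the designated rating. No rate is given. If 5%, 10% or 20% of 150 lacked it (assumed), 142, 135 or 120 pairs would remain, and a two-group comparison on V5 ratings would have 76.7%, 74.6% or 69.5% power (t). Pairs leaving after V3 would keep their V2 and V3 ratings.

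**The case against.** **The trial does collect clean satisfaction data.** This stands. A reader might infer that the fallback has no uncontaminated satisfaction outcome, or that a pair leaving before V5 has no satisfaction data. Section 5.2.2 contradicts both: V2 and V3 ratings of Cup 1 precede use of Cup 2. What is missing is a statement that the fallback will use them. Without it, a substitute for the primary measure would be chosen after order effects had been seen. Blinding the analyst to cup assignment lessens that problem but does not fix the choice in advance.

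**The full crossover analysis is not shown to be biased.** This also stands. A reader might infer that the main comparison sets a recalled rating against a fresh one, to one cup's disadvantage. Order is randomized, so each cup is the recalled one in one sequence and the fresh one in the other. An additive recall difference is then a period effect and need not favour either cup.

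**Rating both cups after using both is a legitimate choice.** Agreed. It gives a common frame of reference for a comparative hypothesis. Making V3 (Cup 1) and V5 (Cup 2) the primary ratings would bring its own asymmetry, since only the second is given with experience of both cups. It would also still leave pairs who go before V5 without that Cup 2 value. The documents do not support replacing the primary measure.

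**The fallback may not have been meant for satisfaction.** Section 3.1 assigns generalized estimating equations to intake, spillage and duration and a sign test to preference, and names no model for rated satisfaction. But the fallback is worded without exception, and Section 2.3 extends its power calculation to satisfaction. If an exemption is intended, it needs to be stated.

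**Conclusion.** The point holds for the fallback. None of the V5 ratings of a first cup (150 pairs, up to 200) is pre-crossover, so dropping second-cup data cannot remove the second cup's influence from the designated primary satisfaction rating. It can for spillage, intake and duration.

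The size of any resulting bias, c_N − c_G, cannot be estimated from the documents, and the problem arises only if design effects are observed. The conclusion rests on the visit order and on where the primary tag is placed. It does not rest on the power figures, which assume equal allocation and a borrowed SD.

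Loss before V5 is a lesser point. Section 4.2 requires an anticipated stay of at least 48 hours and Section 5.3 expects minimal loss.

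**What to change.** Keep the V5 survey rating as the primary satisfaction measure for the full crossover analysis. Add one sentence to Section 3.1, for example: *Any first-cup-only analysis of caregiver satisfaction will use the Feeding Assessment rating of Cup 1 made before crossover (at V3), not the In-Hospital Preference Survey rating.* The mean of V2 and V3 is an acceptable alternative. One of the two should be fixed before the data are examined.

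Cost: one sentence, with no new visit or measurement, since the per-feed rating is already planned.

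Downside: the fallback would rest on a per-feed rating rather than the side-by-side V5 rating. The items and response scales of the two forms are not in the documents and may differ. The sponsor should check this and, if they do differ, report the fallback result on the Feeding Assessment's own scale.

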5.2.3 Case Report Forms

Case report forms will record intervention and outcome data as well as data on other covariates.

Baseline Survey, V1. The baseline intake will record cup assignment, infant weight, length, demographics and infant and maternal feeding and health characteristics (e.g. co-morbidities, type of delivery, etc). It is estimated to take about 10-15 minutes to complete.

Feeding Assessment, V2-V5. This case report form will be used to record outcome information collected on milk intake, spillage and duration of feed and the cup used described below and caregiver's immediate experience using the cup. It will also collect information about prior feedings and time since last feed. Each Feeding Assessment will last as long as the feeding plus about 5 minutes.

In-Hospital Preference Survey, V5. This survey will collect information on the caregiver's experience using both cup and her preferences. It will take about 5 minutes to complete.

Follow-up Survey, V6. This survey will assess cup feeding practices, infant health, and maternal satisfaction with the cup. It will take about 10 minutes to complete.

5.2.4 Other Measures

Infant Weight and Length, V1. We will weigh and measure the length of the infant using standard equipment used in the mother-baby unit. We will follow WHO guidelines on measuring weight and height.¹¹ These procedures will take about 5-10 minutes.

5.2.5 Data Abstraction

Prescreening Log. We will abstract participant information (e.g. name, bed, cup feeding status, etc.) onto the prescreening log in order to track eligibility of potential participants.

Eligibility Checklist. We will abstract and record information about eligibility on this form. Information on the eligibility screener will come from the clinical records, the provider and the caregiver. All eligibility information will be collected prior to determining eligibility and enrolling a participant.

For assessing eligibility related to congenital anomalies, we will refer to a standardized list of minor congenital anomalies.¹³ If the infant has a congenital anomaly, the RA will check the list to determine if it is minor.

Chart Review of Discharge. We will record the date of discharge on a discharge log to determine how long the caregiver has been cup feeding at the time of the Follow-up Survey. To the extent available, we will collect age, weight, and feeding status (current breastfeeding status, cup feeding prescribed and volumes, supplemental feeding if required).

5.3 Retention

Because our study is predominantly conducted in inpatients and is short, we anticipate we will have minimal loss to follow-up.

5.4 Withdrawal

Subjects are free to withdraw from participation in the study at any time upon request. The study team may withdraw subjects who are not compliant with study visits or data collection procedures or who meet an exclusion criterion after enrollment. We may also terminate a study subject's participation in the study if any medical condition, event or situation occurs such that continued participation in the study would not be in the best interest of the subject. If a participant decides to withdraw from the study, we will honor that decision, but will also do our best to understand why the caregiver/parent wishes to withdraw and respond to their concerns. We will document the reason for study withdrawal on a document that tracks study participation that we will maintain in Box.

If we discover a previously unrecognized, exclusionary condition that existed prior to the subject's enrollment in our research, we will not conduct the remaining study procedures and explain that because they are not eligible we are discontinuing their participation. Data generated by ineligible subjects (previously unrecognized) will not be used in our analyses. The caregiver/parent will still be given the Nifty and generic feeding cups, five diapers and the bib cloth used to weigh spillage as a thank you for their time and effort.

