- Infant has other condition or situation that makes them unlikely to be able to comply with study procedures. Examples include the infant anticipated to not be in hospital long enough, infant has a suspected intestinal obstruction, or necrotizing enterocolitis. [provider]
- Infants without a mother, grandmother, or aunt caregiver [provider or caregiver]
- Infant has been enrolled in another study at KATH that would interfere with his/her ability to participate in this study.

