5.1 Visits

5.1.1 Visit 1. Baseline (Day 1, Hour 0)

After the consent process, the RA will conduct the Baseline visit. She will:

- Obtain the random assignment of which cup to introduce first
- Administer the Baseline Survey
- Measure the infant's current weight and length.
- Provide the caregiver with assigned Cup 1 and the instructions for use.

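### Section 5.4 lets a team that knows the cup withdraw randomised pairs for missed visits or data procedures, with no provision to collect the later feeds, the V5 rating or V6

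*Combined protocol and SAP*

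**What the plan says.** Section 5.4 (Withdrawal) provides that the study team "may withdraw subjects who are not compliant with study visits or data collection procedures". The power is discretionary. The section sets no threshold and does not require the decision to be made by someone unaware of the cup. Withdrawal at the caregiver's request and withdrawal in the subject's best interest are covered by separate sentences.

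Section 5.0 has a second rule, in mandatory terms. If problems of health, social circumstance or another kind "prevent either of them from participating in study visits, we will discontinue them from the study". The same section says that visits run in sequence, each finished before the next begins.

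On blinding, Section 3.1 says only: "The data analyst will be blinded to the cup assignment". Under Section 5.1.1 the research assistant obtains the random assignment and must "Provide the caregiver with assigned Cup 1 and the instructions for use". The assistant then observes the feeds at V2 to V5.

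On incomplete data, Section 3.1 counts it a strength that "participants with outcome data for at least one feeding assessment are able to be included in our GEE analyses". It adds: "We will evaluate the potential effect of other missing data on our associations using multiple imputation methods". Section 5.2.2 places rated satisfaction, tagged primary, in the In-Hospital Preference Survey at V5. It also records satisfaction after each observed feed (V2–V5).

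**The concern.** A missed visit or an incomplete form is a data problem, and the analysis plan can already cope with it. Section 5.4 nevertheless allows it to end a pair's participation, and no section says that anything is collected afterwards.

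A pair withdrawn during Cup 1 has no Cup 2 feeds, so it has no within-pair spillage contrast. A pair withdrawn at any time before the survey has no V5 rating, and withdrawal also ends the route to V6. Section 3.1 specifies the GEE for intake, spillage and duration, so it does not recover the V5 rating.

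The people who decide know the cup. If caregivers who struggle with one particular cup are more likely to miss an assessment, or are more readily judged non-compliant, the pairs that reach V5 are a selected group and the satisfaction comparison is biased.

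**Working it through.** **1. What the plan's own power figure implies.** Section 2.3 gives 150 pairs, a difference of 5, SD 11, correlation 0.02 to 0.5, two-sided 0.05 and a paired t-test. I take the 5% as 5 units on the scale of the SD.
- Correlation 0.02: SD of the difference = 11 × √(2 × 0.98) = 15.4. Then 5 / (15.4/√150) = 3.98, and power is 97.7%. The stated 90% is not reproduced; it is a conservative floor that needs only about 102 pairs.
- With 10% of pairs lost (135 left), paired power is 96.3%. Lost precision in the paired analysis is therefore not the issue.
- The 80% figure under carryover does reproduce, as 75 against 75 on the first cup only (79.0%). It would fall to 74.3% with 67 per group, but only if the lost pairs gave no Cup 1 data at all.

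**2. Set-up for selection on the V5 rating.** From the documents: 150 pairs, randomised order, two-sided 0.05. Assumed: 75 pairs per order; normal ratings with equal SD for both cups; no true cup difference; a paired t-test (Section 3.1 names no method for the rating); within-pair correlation ρ of 0.02 to 0.5, borrowed from Section 2.3; share removed p of 3%, 5% or 10%.

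**3. Removal for poor experience with whichever cup came first.** Let c be the amount by which removing the poorest Cup 1 raters raises the mean Cup 1 rating. The mean difference, Nifty minus generic, shifts by +(1−ρ)c in the Nifty-first order and by −(1−ρ)c in the generic-first order. The orders are of equal size, so the shifts cancel. Simulation (20,000 trials per setting) gave mean bias 0.00 and false-positive rates of 4.8% to 5.3%.

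**4. Every removal is a poor rater of one named cup used first.** All removals then fall in one order, so the fraction removed there is q = 2p.
- Shift in that cup's rating: c = φ(z_q)/(1−q).
- Shift in the difference within that order, in SDs of the difference: c × √((1−ρ)/2).
- Weight of that order among retained pairs: w = (1−q)/(2(1−p)).
- Overall shift: δ = w × c × √((1−ρ)/2). In standard errors it is δ × √(150(1−p)).

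Worked case, p = 5% and ρ = 0.02: c = 0.1755/0.90 = 0.195; × 0.70 = 0.1365; w = 67.5/142.5 = 0.474; δ = 0.065; × √142.5 = 0.77 standard errors; false-positive rate 12.0%.

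| Removed | ρ | Shift (SD of difference) | Standard errors | Rate, formula | Rate, simulation |
|---|---|---|---|---|---|
| 3% | 0.5 | 0.031 | 0.37 | 6.6% | 6.3% |
| 3% | 0.02 | 0.043 | 0.52 | 8.1% | 8.5% |
| 5% | 0.5 | 0.046 | 0.55 | 8.6% | 8.9% |
| 5% | 0.02 | 0.065 | 0.77 | 12.0% | 13.7% |
| 10% | 0.5 | 0.078 | 0.90 | 14.8% | 14.8% |
| 10% | 0.02 | 0.109 | 1.26 | 24.4% | 25.4% |

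The simulations remove whole pairs (4, 8 and 15 of 150). Repeated runs give about 6–8%, 9–14% and 15–26%.

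**The case against.** The strongest case on the other side is that the clause will seldom be used and seldom matter. Participants are inpatients, the visit windows are minimum intervals with no upper limit, and the research assistant checks in until the required feeds have taken place, so an assessment is more often late than missed. Section 5.3 expects minimal loss and Section 5.4 records reasons for withdrawal. Multiple imputation is planned, and satisfaction recorded after each completed feed could serve as a predictor of a missing V5 rating. All of this stands and limits the likely size. It does not remove the point. No imputation model is given, standard imputation does not correct removal that depends on ratings never observed, and recording a reason does not recover a rating.

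Three stronger readings are tempting and are not supported.
- A reader might infer that a withdrawn pair's existing data are thrown away. The only stated data-exclusion rule in Section 5.4 covers pairs later found to have been ineligible.
- A reader might take as the bound the removal of the pairs that most favoured one cup on the full Nifty-minus-generic rating. That gives false-positive rates of about 15%, 30% and 77% at 3%, 5% and 10% removed. But that difference cannot be known when a pair is removed during Cup 1, because Cup 2 has not been used.
- A reader might add the route for pairs that meet an exclusion criterion after enrolment, since Section 4.2 says "Examples include the infant anticipated to not be in hospital long enough". Section 5.0 states that infants are not kept in hospital for the study, so an early discharge loses the remaining in-hospital feeds whatever Section 5.4 says. At most V6 is recoverable. The same exclusion item also lists medical conditions, so it cannot be called purely administrative.

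**Conclusion.** The point holds as a gap in continued data collection. The plan permits removal on a ground that its own analysis does not require, and provides for nothing to be collected afterwards. That later data are lost is implied by withdrawal and by the absence of any such provision; it is not stated outright.

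Bias is possible but not demonstrated. It is nil under step 3. Under step 4, where every removal concerns one named cup, the false-positive rate on the V5 rating rises from 5% to about 6–8%, 9–14% or 15–26%. A milder pattern does less: if pairs that fared worse on one cup are removed twice as often as the others, the rate is 5.3% at 5% removed and 6.4% at 10%. All of these rest on assumed removal rates, normal ratings and no true cup difference. The change is worth making because it is cheap, not because a large bias has been shown.

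**What to change.** In Section 5.4, delete non-compliance with visits or data collection as a ground for withdrawal by the study team. State instead that a missed or incomplete Feeding Assessment is a missing feed, that the pair keeps its randomised cup order, and that it is offered all remaining visits. State that the V5 survey and V6 are attempted where possible; Section 5.1.7 already allows V6 by telephone, which serves after an early discharge.

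Reconcile Section 5.0 with this. Its discontinuation sentence and its rule that each visit is finished before the next should be worded so that a missed visit alone does not end data collection.

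Leave unchanged the caregiver's right to withdraw, the best-interest clause, the health-related exclusions and discharge practice.

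The cost is protocol wording, a little research-assistant time spent approaching pairs that have missed a visit, and some pairs with partial data.
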